5.4 Concomitant Medications/Treatments

Systemic corticosteroids greater than the equivalent of 10mg of prednisone or equivalent alternative steroid (except physiologic dose for adrenal replacement therapy) or other immunosuppressive agents (such as cyclosporine or methotrexate) and any other medications that could potentially impact the efficacy or safety of the study as judged by the treating investigator are NOT permitted from time of registration to subjects completing protocol therapy unless clinically indicated to manage adverse events or life threatening or serious conditions as determined by the treating investigator. Additional palliative radiation for pain, bleeding, airway compromise, or other needs is permitted.

5.5 Other Modalities or Procedures

Pembrolizumab should be held for any surgery until subject is judged to be stable to resume by treating investigator as adequate information does not exist on its effects on wound healing. When resumed, same dose level will be maintained. Percutaneous procedures like imaging guided biopsies and central line placements do not require pembrolizumab to be held.

5.6 Duration of Therapy

In the absence of treatment delays due to adverse events, treatment will continue for 17 cycles or until one of the following criteria apply:

- Disease progression as defined in Section 7.0
- Patients may continue on pembrolizumab beyond the first progression by imaging as long as investigator deemed clinical benefit continues
- Inter-current illness that prevents further administration of treatment
- Unacceptable adverse event(s) or death
- Patient voluntarily withdraws from treatment
- General or specific changes in the patient's condition render the patient unacceptable for further treatment in the judgment of the investigator

5.7 Off Treatment Criteria

Patients will be removed from protocol therapy when any of the criteria listed in Section 5.6 apply. Document in the source the reason for ending protocol therapy and the date the patient was removed from treatment. All patients who discontinue treatment should comply with protocol specific follow-up procedures as outlined in Section 5.8. The only exception to this requirement is when a subject withdraws consent for all study procedures or loses the ability to consent freely.

5.8 Duration of Follow-Up

Continued follow-up after end of treatment is for patients who discontinue study treatment for reasons other than progressive disease or death (such as patients who discontinue treatment due to toxicity) AND patients who continue on treatment past 17 cycles. These patients should continue to be followed by imaging every 12 weeks with standard of care CT chest, abdomen/pelvis until documentation of progressive disease, death, withdrawal of consent, or initiation of a new anti-cancer treatment for up to 2 years.

5.9 Off Study Criteria

Patients can be taken off study at any time at their own request, or they may be withdrawn at the discretion of the investigator for safety, behavioral or administrative reasons. The reason(s) for discontinuation from study will be documented and may include:

- Patient withdraws consent (termination of treatment and follow-up);
- Loss of ability to freely provide consent through imprisonment or involuntary incarceration for treatment;
- Patient is unable to comply with protocol requirements;
- Treating physician judge's continuation on the study would not be in the patient's best interest;
- Patient becomes pregnant (pregnancy to be reported along same timelines as a serious adverse event);
- Development of second malignancy (except for basal cell carcinoma or squamous cell carcinoma of the skin) that requires treatment, which would interfere with this study;
- Lost to Follow-up. *If a research subject cannot be located to document progression free survival after a period of 2 years, the subject may be considered "lost to follow-up." All attempts to contact the subject during the two years must be documented.*
- Termination of the study by The University of Michigan;
- Patient completes protocol treatment and follow-up criteria.

5.10 Patient Replacement

A patient is evaluable for feasibility and safety if they receive at least one dose of pembrolizumab. Patients who achieve a complete response prior to SBRT are not evaluable for feasibility. Non-evaluable patients will be replaced.

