8.1	Adverse Event Reporting Requirements	34
8.2	Definitions	35
8.3	Adverse Event Characteristics	36
8.4	Serious Adverse Event Reporting Guidelines	37
8.5	Routine Reporting	37
8.6	Reporting of Unanticipated Problems	37
9.0	DRUG INFORMATION	38
9.1	Pembrolizumab	38
10.0	CORRELATIVES/SPECIAL STUDIES	39
10.1	Sample Collection Guidelines	39
10.2	Specimen Banking	40
11.0	STATISTICAL CONSIDERATIONS	40
11.1	Study Design/Study Endpoints/ Sample Size & Accrual	40
11.2	Data Analyses Plans	41
12.0	DATA AND SAFETY MONITORING	41
13.0	REFERENCES	42

ABBREVIATIONS

AE	Adverse Event
ALT	Alanine Aminotransferase
ALC	Absolute Lymphocyte Count
Anti-PD(L)1	Anti-Programmed Death (Ligand) 1
AST	Aspartate Aminotransferase
BUN	Blood Urea Nitrogen
CBC	Complete Blood Count
CMP	Comprehensive Metabolic Panel
CR	Complete Response
CT	Computed Tomography
CTCAE	Common Terminology Criteria for Adverse Events
CTSU	Clinical Trials Support Unit
DLT	Dose Limiting Toxicity
DSMC	Data and Safety Monitoring Committee
H&P	History & Physical Exam
HRPP	Human Research Protections Program
IND	Investigational New Drug
IRB	Institutional Review Board
IV (or iv)	Intravenously
MTD	Maximum Tolerated Dose
NCI	National Cancer Institute
ORR	Overall Response Rate
OS	Overall Survival
PBMCs	Peripheral Blood Mononuclear Cells
PD	Progressive Disease
PFS	Progression Free Survival
PI	Principal Investigator
p.o.	per os/by mouth/orally
PR	Partial Response
PRC	Protocol Review Committee
SAE	Serious Adverse Event
SBRT	Stereotactic Body Radiation Therapy
SD	Stable Disease
SGOT	Serum Glutamic Oxaloacetic Transaminase
SPGT	Serum Glutamic Pyruvic Transaminase
UaP	Unanticipated Problem
UMCCC	University of Michigan Comprehensive Cancer Center
WBC	White Blood Cells

STUDY SCHEMA

SBRT and Anti-PD(L)1 Schedule

[figure not shown]

Figure 1: Study Schema. Abbreviations: Anti-PD(L)1=Pembrolizumab in this trial, Anti-PD(L)1 Cycle Length= 3 weeks *Imaging will occur at week 12 +/- 7 days

STUDY SYNOPSIS

Title	FAST: Feasibility trial of Anti-PD(L)1 and SBRT in the Treatment of Advanced, Platinum-Refractory Urothelial Carcinoma
Phase	Feasibility
Methodology	Single Arm
Study Duration	12 months treatment, up to 24 months follow-up
Study Center(s)	University of Michigan

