it has not been extensively evaluated in patients treated with new immunotherapies and new forms of radiation such as stereotactic body radiation therapy (SBRT). In a small phase one study, the combination of Interleukin-2 (IL-2) and SBRT led to a substantially improved response rate compared to historical controls in patients with melanoma and kidney cancer [14]. Case reports have shown similar responses with newer immunotherapy drugs such as ipilimumab, an anti-CTLA4 drug [12]. Given these encouraging results, the concept of combining SBRT with immunotherapy warrants further evaluation with newer immunotherapeutics such as pembrolizumab that are more widely applicable than IL-2.

We propose a single-center feasibility trial to study the combination of SBRT with pembrolizumab in patients with metastatic urothelial carcinoma who have progressed on or within 12 months of platinum based chemotherapy. One dose of pembrolizumab will be given followed by SBRT to at least 1 amenable lesion chosen at the discretion of the radiation oncologist. This will be followed by three further cycles of pembrolizumab before the patient is assessed radiographically. Subjects must have RECIST 1.1 measurable disease in addition to the lesion proposed to be treated with SBRT.

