5.0 TREATMENT PLAN

5.1 Treatment Dosage and Administration

Protocol treatment must start within 14 business days of enrollment to the study.

5.1.1 Therapy will include pembrolizumab 200 mg IV starting on day 1 in 21 day cycles. Patients will receive 1 dose (cycle 1) of pembrolizumab and commence SBRT no later than initiation of cycle 2.

5.1.2 SBRT will be given to ≥ 1 metastatic lesion(s) deemed most appropriate for such therapy by the treating radiation oncologist. SBRT will be delivered in 3 or 5 fractions with dose and fractionation selected to respect standard normal tissue dose constraints for adjacent organs at risk. See section 5.3 for further details.

5.1.3 The lesion to which SBRT is given will be identified after the patient receives 1 dose of pembrolizumab

5.1.3 Patients will be treated with supportive care pre-medications as clinically indicated including anti-emetics.

REGIMEN DESCRIPTION					
Agent	Premedications	Dose	Route	Schedule	Cycle Length
Pembrolizumab	None mandated	200 mg	IV	Once every 21 days (+/- 3 business days)	
SBRT	None mandated	3-5 fractions with dose and fractionation selected to respect standard normal tissue dose constraints for the relevant organs in the vicinity of the target lesion(s).	n/a	In cycle 1 any time after D1 and will commence no later than initiation of cycle 2	

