Complete Response (CR): Disappearance of all target lesions, determined by two separate observations conducted not less than 4 weeks apart. There can be no appearance of new lesions.

Partial Response (PR): At least a 30% decrease in the sum of the longest diameter (LD) of target lesions, taking as reference the baseline sum LD. There can be no appearance of new lesions.

Progressive Disease (PD): At least a 20% increase in the sum of the LD of target lesions, plus a minimum 5 mm increase, taking as reference the smallest sum LD recorded since the treatment started, or the appearance of one or more new lesions.

Stable Disease (SD): Neither sufficient shrinkage to qualify for PR nor sufficient increase to qualify for PD, taking as reference the smallest sum LD since the treatment started.

Evaluation of Non-Target Lesions

Complete Response (CR): Disappearance of all non-target lesions and normalization of tumor marker level.

Incomplete Response/Stable Disease (SD): Persistence of one or more non-target lesion(s) and/or maintenance of tumor marker level above the normal limits.

Progressive Disease (PD): Appearance of one or more new lesions and/or unequivocal progression of existing non-target lesions.

Evaluation of Best Overall Response

The best overall response is the best response recorded from the start of the treatment until disease progression/recurrence (taking as reference for progressive disease the smallest measurements recorded since the treatment started). The patient's best response assignment will depend on the achievement of both measurement and confirmation criteria.

Target Lesions	Non-Target Lesions	New Lesions	Overall Response	Best Response for this Category Also Requires:
CR	CR	No	CR	≥4 wks. confirmation
CR	Non-CR/SD	No	PR	≥4 wks. confirmation
PR	Non-PD	No	PR	
SD	Non-PD	No	SD	Documented at least once ≥4 wks. from baseline
PD	Any	Yes or No	PD	no prior SD, PR or CR
Any	PD*	Yes or No	PD	
Any	Any	Yes	PD	
* In exceptional circumstances, unequivocal progression in non-target lesions may be accepted as disease progression.				

Note: Patients with a global deterioration of health status requiring discontinuation of treatment without objective evidence of disease progression at that time should be reported as “*symptomatic deterioration*”. Every effort should be made to document the objective progression even after discontinuation of treatment.

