11.0 STATISTICAL CONSIDERATIONS

11.1 Study Design/Study Endpoints, Sample Size and Accrual

The primary aim of this study is to determine the feasibility of treating patients with metastatic urothelial carcinoma who have progressed after platinum based chemotherapy with sequential pembrolizumab and SBRT. Treatment success will be defined as completion of 4 cycles of pembrolizumab and at least one course of treatment of SBRT within 15 weeks from first dose of pembrolizumab. The trial will define the combination treatment as feasible if 70% of the patients receive the treatment as defined. With 20 evaluable patients, if 14 out of 20 (70% [95% Confidence Interval: 50% - 90%]) achieve successful treatment then the trial will conclude that further evaluation of sequential pembrolizumab and SBRT should be explored. A patient is evaluable for feasibility and safety if they receive at least one dose of pembrolizumab. Patients who achieve a complete response prior to SBRT are not evaluable for feasibility. Non-evaluable patients will be replaced. With accrual of 1-2 patients per month the trial accrual is expected to take up to 24 months.

Secondary endpoints will include efficacy and safety. Efficacy will be measured using the following endpoints: best overall response by RECIST and Immune Related Response Criteria and progression-free survival by RECIST and Immune Related Response Criteria. Safety endpoints will measure the frequency and severity of grade 3-5 drug-related adverse events of the combination of SBRT and pembrolizumab.

Correlative plans are described separately below.

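### The exclusion and replacement of patients with a complete response before SBRT has no scheduled assessment behind it and no time limit, so in practice it removes mainly patients whose SBRT was late or never given

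*Combined protocol and SAP*

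**What the plan says.** Sections 5.10 and 11.1 make any patient with at least one pembrolizumab dose evaluable for feasibility, with one exception: "Patients who achieve a complete response prior to SBRT are not evaluable for feasibility. Non-evaluable patients will be replaced." The synopsis repeats the rule. None of the three places says how a CR before SBRT is to be established, by when, or whether it must be confirmed.

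Four other provisions bear on the rule:

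- **SBRT timing (5.1):** "Patients will receive 1 dose (cycle 1) of pembrolizumab and commence SBRT no later than initiation of cycle 2." Cycles last 21 days, with a window of 3 business days either way.
- **Imaging:** the schema footnote says "Imaging will occur at week 12 +/- 7 days". The Time and Events Table (6.2) lists no tumor measurement between screening and week 12. Section 1.3, after describing SBRT, says: "This will be followed by three further cycles of pembrolizumab before the patient is assessed radiographically."
- **CR definition (7.1):** "Disappearance of all target lesions, determined by two separate observations conducted not less than 4 weeks apart."
- **Primary endpoint (2.4, 11.1, 11.2):** four cycles of pembrolizumab plus SBRT within 15 weeks of the first dose. The combination is called feasible at 14 of 20, given as 70% with a 95% confidence interval of 50% to 90%.

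**The concern.** The rule removes patients from the denominator because of something that happens after treatment starts. That could be harmless if it picked out a clear group by a planned assessment: patients who responded so early that nothing was left to irradiate when SBRT fell due. The schedule contains no assessment that could identify them at that point.

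The rule also has no end date. A patient whose SBRT slipped or was dropped, and who is later found to be in CR, fits the words of the exclusion. If that patient has had no SBRT by week 15, the primary endpoint has been missed, yet the patient leaves the count and another is enrolled. With a fixed threshold of 14 of 20, that gives the trial a second try at a success.

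**Working it through.** **The plan's own figure.** 0.70 ± 1.96 × √(0.70 × 0.30 / 20) = 0.70 ± 0.201, or 49.9% to 90.1%. This reproduces the stated 50% to 90%; it is the normal-approximation interval.

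**Timeline, in days after the first dose.**

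| Event | Source | Day |
|---|---|---|
| Cycle 2, and so the SBRT deadline | 5.1 | 21 |
| Cycle 2 at the end of its window (3 business days, at most 5 calendar days) | 5.1 | 26 |
| Earliest two post-dose observations 28 days apart, even with unscheduled scans | 7.1: 1 + 28 | 29 |
| First scheduled scan | schema, 6.2 | 84 |
| First scan at the early edge, 7 days | schema | 77 |
| First scan at the early edge, 7 business days (9 to 11 calendar days) | 6.2 | 73 to 75 |

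Day 29 is later than day 26, so a CR meeting the two-observation definition cannot exist before SBRT if cycle 2 is not delayed. On scheduled scans, the first at week 12 and confirmation 4 weeks later, it falls at week 16. It falls at week 15.0 with the 7-day window and at weeks 14.4 to 14.7 with the 7-business-day window. The two imaging windows differ and should be reconciled.

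The SBRT planning CT does not fill the gap. Section 5.3.2 requires it to cover only the treated region and nearby organs, while 3.1.2 requires measurable disease outside the SBRT target.

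**Effect on the count.** Suppose there are 13 successes in 20, which is 65% and below the criterion. Drop one failure as a CR before SBRT and add a replacement who succeeds: 14/20 = 70%, feasible. Conversely, take 14/20 as reported and put the excluded patients back as failures:

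- 1 excluded: 14/21 = 66.7%
- 2 excluded: 14/22 = 63.6%
- 3 excluded: 14/23 = 60.9%

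Reaching 70% would then take 15/21, 16/22 or 17/23.

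**Chance of a flip.** The documents give no CR rate for pembrolizumab (the 21% in 1.1 is all responses), so the excluded fraction c is an assumption. Take a true success rate of 60% and assume that every excluded patient would have failed.

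- P(exactly 13 of 20) = 0.166. It is 0.184 at a true rate of 65% and 0.164 at 70%.
- With c = 2% of all patients and 40% failing, 0.02 / 0.40 = 5% of failures are excludable. P(at least one among 7 failures) = 1 − 0.95⁷ = 0.30.
- P(replacement succeeds) is about 0.60.
- Joint chance: 0.166 × 0.30 × 0.60 = 0.030, about 3%.
- With c = 0.5%: 0.005 / 0.40 = 1.25%; 1 − 0.9875⁷ = 0.084; 0.166 × 0.084 × 0.60 = 0.008, under 1%.

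The whole effect follows by replacing the success rate p with p / (1 − c) and computing P(at least 14 of 20):

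| True rate | No exclusion | c = 2% | c = 5% | c = 10% |
|---|---|---|---|---|
| 60% | 25.0% | 28.7% | 35.1% | 47.9% |
| 70% | 60.8% | 66.2% | 74.3% | 86.4% |

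At 60% and c = 2% the gain is 28.7 − 25.0 = 3.7 percentage points, in line with the 3% from the single-patient route. The 10% column is probably unrealistic and is shown as an upper limit.

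**The case against.** The rule is prespecified and worded consistently in all three places. It also has a sensible purpose: a patient with nothing left to irradiate tells us little about whether SBRT can be delivered, and counting that patient as a failure changes what is being estimated. That is fair, and it is a real cost of the fix. But an estimate restricted to patients who still have a target needs a planned way to identify them when SBRT is due, and the plan has none.

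A reader might infer four stronger statements, none of which the documents support.

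- **The rule can never apply to a patient treated on schedule.** Section 5.10 does not cite 7.1 or require confirmation, so a single unscheduled scan in cycle 1 showing CR would trigger it. Section 7.1 itself allows for progression found before the end of cycle 1, so early assessment is not barred. The SBRT deadline also moves with cycle 2, and 5.2 lets pembrolizumab be held for up to 12 weeks from the prior dose. With a held cycle 2, two observations 28 days apart could precede on-time SBRT.
- **It removes only SBRT-timing failures.** The endpoint deadline is week 15, not cycle 2. SBRT that starts after cycle 2 but is given by week 15 can still count as success, and a patient with no lesion left is not a timing failure.
- **It can only raise the proportion.** The exclusion applies whether or not SBRT follows. A patient in CR who then completes SBRT and four cycles by week 15 would be a success removed from the count.
- **The chance of a changed conclusion is 16% to 18%.** That is only the chance of landing on 13 of 20. An excludable failure and a successful replacement are needed as well.

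**Conclusion.** The concern holds in limited form. No scheduled assessment can trigger the exclusion when cycle 2 and SBRT are on time. Apart from a held cycle 2 or an unscheduled single scan, the rule reaches patients whose SBRT was late or not given. Followed exactly, it can drop and replace someone who never received the sequence, so the bias is usually, though not strictly always, upward.

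The expected size is small. The flip chance of about 3% rests on an assumed 2% excluded and a true success rate of 60%, and it falls below 1% if 0.5% are excluded. The matter still merits a change: the threshold is fixed, a single patient at the boundary decides the conclusion, and the correction needs no new data.

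**What to change.** Base the primary feasibility proportion on every patient given at least one dose of pembrolizumab, with no replacement for CR. Count a patient without SBRT by week 15 as not successful, and report descriptively how many had no SBRT because of response. This means changing the exclusion wording in the synopsis, 5.10 and 11.1, with the analysis population in 11.2 stated to match.

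If the sponsor keeps the exclusion, limit it to a CR documented by a stated method before the SBRT deadline, and say whether confirmation is required. Report the all-treated proportion beside the primary result and apply the 70% criterion to it.

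The cost is a few sentences. The proportion may be slightly less favourable, and a complete responder with nothing left to irradiate will count as not having received the sequence. The descriptive line lets readers see how many such patients there were.

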6.0 STUDY PROCEDURES

6.1 Follow-Up Procedures

Continued follow-up after end of treatment is for patients who discontinue study treatment for reasons other than progressive disease or death (such as patients who discontinue treatment due to toxicity) AND patients who continue on treatment past 17 cycles. These patients should continue to be followed by imaging every 12 weeks with standard of care CT chest, abdomen/pelvis until documentation of progressive disease, death, withdrawal of consent, or initiation of a new anti-cancer treatment for up to 2 years.

6.2 Time and Events Table

All assessments have a window of \pm 5 business days except for imaging/tumor measurements where a window of \pm 7 business days will apply.

Study Calendar

	Screening period (within 28 days)	C1 D1 ¹	SBRT (will commence no later than initiation of cycle 2) ³	C2 D1	C3 D1	C4 D1	Week 12	C5 D1	Cycles per std frequency for drug Every 12 weeks	End of Treatment	Follow-up (every 12 weeks for up to 24 months) ⁵
Informed Consent for FAST	X										
Informed Consent for MI-Oncoseq ⁴	X										
Archival Tissue identified	X										
Serum and Plasma banking	X ²										
Optional Biopsy at Progression										X	
History and Physical	X	X		X	X	X		X	X	X	
ECOG PS	X	X		X	X	X		X	X	X	
Tumor Measurements	X						X			X	X
Toxicity Evaluation	X	X		X	X	X		X	X	X	
CBC with diff and platelet count	X	X		X	X	X		X	X	X	
Comp metabolic panel	X	X		X	X	X		X	X	X	
Amylase/Lipase	X							X		X	
TSH, free T3, free T4 (IF clinically indicated: FSH, LH, ACTH)	X							X		X	
HIV, Hepatitis B Surface Antigen	X										
Pregnancy test for WOCBP	X										
CT Chest	X						X			X	X

CT or MRI Abdomen/Pelvis	X						X			X		X
Pembrolizumab		X		X	X	X		X	X			
SBRT			X									

¹Cycles are 21 days in duration.

² Serum and plasma banking will be collected C1D1 prior to first dose

³SBRT cannot overlap with C1D1

⁴Optional

⁵ Continue follow-up after end of treatment is for patients who discontinue study treatment for reasons other than progressive disease or death AND patients who continue on treatment past 17 cycles. These patients should continue to be followed by imaging every 12 weeks with standard of care CT chest, abdomen/pelvis until documentation of progressive disease, death, withdrawal of consent, or initiation of a new anti-cancer treatment for up to 2 years.

